## 2. INTRODUCTION

This SAP provides the detailed methodology for summary and statistical analyses of the data collected in study B1641003. This document may modify the plans outlined in the protocol; however, any major modifications of the primary endpoint definition or its analysis will also be reflected in a protocol amendment.

Statistical analyses will be performed using cleaned eCRF data as well as non-CRF data (ie, biomarker data, PK data). The primary analysis will include all data up to a clinical cut-off date corresponding to 24 months (104 weeks) after the last patient receive the first dose of the study drug. The final analysis of the data will be performed after last patient last visit (LPLV).

Additional analyses of the data may be performed for publication or regulatory reporting purposes.

Throughout this document ‘start date’ refers to first dose of study treatment.

### 2.1. Study Objectives

#### Primary Objectives

- To estimate the Maximum Tolerated Dose (MTD) and select the Recommended Phase 2 Dose (RP2D) for the combination of PF-05082566 with MK-3475 in patients with advanced solid cancer.

#### Secondary Objectives

- To evaluate the overall safety profile;
- To characterize the single dose and multiple dose pharmacokinetics (PK) of PF-05082566 and MK-3475 given in combination following IV administration;
- To evaluate the immunogenicity of PF-05082566 and MK-3475 when given in combination;
- To assess the anti-tumor effect of PF-05082566 in combination with MK-3475 (by RECIST criteria);
- Expansion Cohorts Only:** To characterize the mechanism of sensitivity and/or resistance to PF-05082566 in combination with MK-3475 in tumor tissue.

CCI [REDACTED]

- CCI [REDACTED]
- CCI [REDACTED]

## 2.2. Study Design

This is a Phase 1b, open-label, multi-center, multiple-dose, safety, pharmacokinetic CCI [REDACTED] study designed to estimate the MTD, and determine the RP2D of PF-05082566 in combination with MK-3475 in patients with advanced solid tumors.

PF-05082566 will be administered as a 1-hour intravenous infusion q3wks. On Day 1 of each dosing cycle, in which the drugs are co-administered, the MK-3475 infusion will start 30 minutes after completion of PF-05082566 infusion and after the post- PF-05082566 and pre-MK-3475 PK blood samples are drawn.

Treatment with study drugs will continue until completion of 32 cycles (approximately 24 months) of treatment, confirmed objective disease progression, patient refusal, patient lost to follow up, unacceptable toxicity occurs, or the study is terminated by the Sponsor, whichever occurs first.

Once the MTD of PF-05082566 administered in combination with MK-3475 has been estimated with confidence, one or more expansion cohorts of patients with selected advanced solid tumors will be enrolled to further study the safety, tolerability, PK CCI [REDACTED] and preliminary anti-tumor activity for PF-05082566 in combination with MK-3475 to support RP2D selection, as well as to study tumor-associated biomarkers. The tumor types for further study could include NSCLC and potentially other tumor types based on emerging data from the dose escalation phase of this study.

Antitumor activity will be assessed by radiological tumor assessments conducted at baseline, at 9 weeks after the first dose of study drug, and every 6 weeks thereafter, whenever disease progression is suspected (eg, symptomatic deterioration), and at the time of End of Treatment/Withdrawal (if not done in the previous 6 weeks), using RECIST v1.1. Safety will be monitored at regular intervals throughout the study by means of laboratory tests and clinical visits. PK CCI [REDACTED] blood endpoints will also be monitored in all patients.

For all patients in dose-expansion cohorts, a de novo biopsy will be required at study entry followed by a second biopsy at the time of the week 9 scans (after 3 cycles of treatment). Optional de novo biopsies may be collected from patients in dose-escalation cohorts to support the assessment of disease progression. CCI [REDACTED]

### **3. ENDPOINTS AND BASELINE VARIABLES: DEFINITIONS AND CONVENTIONS**

#### **3.1. Primary Endpoints**

- First 2 cycles Dose-Limiting Toxicity (DLT) of PF-05082566 in combination with MK-3475.

Severity of adverse events (AEs) will be graded according to CTCAE v 4.03. any of the following AEs occurring during the DLT observation period (first 2 Cycles, ie, 6 weeks) that are attributable to one or both study drugs will be classified as DLTs:

- Hematologic:
  - Grade 4 neutropenia;
  - Febrile neutropenia, defined as absolute neutrophil count (ANC)  $<1000/\text{mm}^3$  with a single temperature of  $>38.3$  degrees C (101 degrees F) or a sustained temperature of  $\geq 38$  degrees C (100.4 degrees F) for more than one hour;
  - Grade  $\geq 3$  neutropenic infection;
  - Grade  $\geq 3$  thrombocytopenia with bleeding;
  - Grade 4 thrombocytopenia.
- Non-hematologic:
  - Grade  $\geq 3$  toxicities (non-laboratory);
  - Grade  $\geq 3$  nausea, vomiting or diarrhea despite maximal medical therapy;
  - Grade 4 aspartate aminotransferase (AST) and alanine aminotransferase (ALT).
- Other (non AST/ALT) non-hematologic Grade  $\geq 3$  laboratory value if:
  - Medical intervention is required to treat the patient, or
  - The abnormality leads to hospitalization.
- Inability to complete two infusions of MK-3475 and PF-05082566 during the DLT observation period.

## 3.2. Secondary Endpoints

### 3.2.1. Safety Endpoints

- Adverse Events as characterized by type, severity (as graded by NCI CTCAE v.4.03), timing, seriousness, and relationship to study therapy PF-05082566 in combination with MK-3475;

AEs will be graded by the investigator according to the CTCAE version 4.03 and coded using the Medical Dictionary for Regulatory Activities (MedDRA)

- Laboratory abnormalities as characterized by type, severity (as graded by NCI CTCAE v.4.03);
- Vital signs, weight, ECOG Performance Status.

### 3.2.2. Efficacy Endpoints

- Objective tumor response by RECIST v1.1;

OR is defined as complete response (CR) or partial response (PR) according to RECIST v1.1 from ‘start date’ until documented disease progression. Both CR and PR must be confirmed by repeat assessments performed no less than 4 weeks after the criteria for response are first met.

- Time-to-response (TTR, expansion cohorts only);

TTR is defined, for patients with an objective response, as the time from the ‘start date’ to the first documentation of objective response (CR or PR) which is subsequently confirmed.

- Duration of response (DR, expansion cohorts only);

DR is defined, for patients with an objective response, as the time from first documentation of objective response (CR or PR) to the date of first documentation of objective progression of disease (PD) or death due to any cause.

- Progression-free survival (PFS, expansion cohorts only);

PFS is defined as the time from ‘start date’ to the date of the first documentation of PD or death due to any cause, whichever occurs first.

### 3.2.3. Pharmacokinetic Endpoints

- PK parameters of PF-05082566 and MK-3475, including but not limited to Cmax, Ctrough, Tmax, AUC0-last, CL and Vd (as data permits);

**Table 2. PK Parameters to be Determined for PF-05082566 and MK-3475**

Parameter	Definition	Method of Determination
$AUC_{last}$	Area under the serum concentration-time profile from time zero to the time of the last quantifiable concentration ( $C_{last}$ )	Linear/Log trapezoidal method
$AUC_{\tau}$	Area under the serum concentration-time over dosing interval $\tau$	Linear/Log trapezoidal method
$C_{max}$	Maximum observed serum concentration	Observed directly from data
$T_{max}$	Time for $C_{max}$	Observed directly from data as time of first occurrence
$t_{1/2}^a$	Terminal half-life	$\text{Log}_e(2)/k_{el}$ ,  where $k_{el}$ is the terminal phase rate constant calculated by a linear regression of the log-linear concentration-time curve. Only those data points judged to describe the terminal log-linear decline were used in the regression.
$C_{trough}$	Predose concentration during multiple dosing	Observed directly from data
CL	Clearance	Dose / $AUC_{\tau}$ for steady state
$V_d^a$	volume of distribution	Dose / ( $AUC_{\tau} \cdot k_{el}$ ) for steady state
$AUC_{last}(dn)$	Dose normalized $AUC_{last}$	$AUC_{last} / \text{Dose}$
$AUC_{\tau}$	Dose normalized $AUC_{\tau}$	$AUC_{\tau} / \text{Dose}$
$C_{max}(dn)$	Dose normalized $C_{max}$	$C_{max} / \text{Dose}$

a If data permit

### 3.2.4. Immunogenicity Endpoints

- Anti-Drug Antibody (ADA)/Neutralizing antibodies (Nab) titers for PF-05082566 and MK-3475.

### 3.2.5. Biomarker Endpoints

- Expansion Cohorts Only: Paired de novo tumor biopsy collection at sequential time points for analysis of exploratory mechanistic biomarkers such as IHC assessment of tumor-infiltrating lymphocytes, quantitation of T cell receptor sequences, and gene expression.

CCI

- CCI

- CCI

### 3.4. Baseline Variables

#### 3.4.1. Study Drug, Study Treatment and Baseline Definitions

In this study, ‘**study drug**’ refers to PF-05082566 or MK-3475 and ‘**study treatment**’ (or ‘**treatment group**’) refers to one of the following:

- Cohort -1: PF-05082566 0.2 mg/kg q3wks + MK-3475 2mg/kg q3wks;
- Cohort 1: PF-05082566 0.45 mg/kg q3wks + MK-3475 2mg/kg q3wks;
- Cohort 2: PF-05082566 0.9 mg/kg q3wks + MK-3475 2mg/kg q3wks;
- Cohort 3: PF-05082566 1.8 mg/kg q3wks + MK-3475 2mg/kg q3wks;
- Cohort 4: PF-05082566 3.6 mg/kg q3wks + MK-3475 2mg/kg q3wks;
- Cohort 5: PF-05082566 5 mg/kg q3wks + MK-3475 2mg/kg q3wks.

**Start of study treatment** is the first dose of study drug administered.

#### Definition of baseline:

The last available assessment prior to the start of study treatment is defined as ‘baseline’ value or ‘baseline’ assessment for safety and efficacy analyses. If an assessment is planned to be performed prior to the first dose of study treatment in the protocol and the assessment is performed on the same day as the first dose of study treatment, it will be assumed that it was performed prior to study treatment administration, if assessment time point is not collected or is missing. If assessment time points are collected, the observed time point will be used to determine pre-dose on study day 1 for baseline calculation. Unscheduled assessments will be used in the determination of baseline. However, if time is missing, an unscheduled assessment on study day 1 will be considered to have been obtained after study treatment administration.

Patients who start treatment and discontinue from the study on the same day may have two different sets of data collected on study day 1 (one during study and one in the End of Treatment (EOT) visit. Data reported at the EOT visit are not eligible for baseline selection.

If a scheduled pre-dose measurement actually occurred post-dose, then the corresponding measurement will be treated and analyzed similar to an unscheduled post-dose measurement.

Baseline for heart rate (HR) and QT/QTc interval assessments will be derived from the visit where both HR and QT are not missing. Triplicate ECGs are collected in the study and the baseline for each ECG measurement is the average of the pre-dose replicate measurements on the baseline day. Unscheduled assessments will not be included in the calculation of the average. QTcB and QTcF will be derived based on HR and QT. The average of the replicate measurements will be determined after the derivation of the individual parameter at each time point.

### **3.4.2. Baseline Characteristics**

Baseline characteristics (including demographics, physical measurements, disease history and prior anti-cancer therapies) are described in [Section 6.5.1](#). These baseline characteristics are not planned to be included as stratification variables or covariates in statistical models unless otherwise specified in [Section 6](#).

## **3.5. Safety Endpoints**

### **3.5.1. Adverse Events**

#### **Treatment-Emergent Adverse Events**

Treatment-emergent adverse events (TEAEs) are those events with onset dates occurring during the on-treatment period for the first time, or if the worsening of an event is during the on-treatment period.

**On-treatment period** is defined as the time from the first dose of study treatment through minimum (30 days + last dose of study treatment, start day of new anti-cancer drug therapy – 1 day). The start day of new anti-cancer drug therapy after the first dose of study treatment is derived as outlined in [Section 5.2.5](#).

#### **Adverse Events of Special Interest (AESIs)**

AESIs are immune-related adverse events (irAE) and infusion-related reactions (IRRs). The criteria for classification of an AE as an irAE or IRR are documented separately in the pembrolizumab Event of Clinical Interest (ECI) document.

## **4. ANALYSIS SETS**

Data for all patients will be assessed to determine if patients meet the criteria for inclusion in each analysis population prior to releasing the database and classifications will be documented per Pfizer's standard operating procedures.

Only patients who signed informed consent will be included in the analysis sets below.

#### **4.1. Full Analysis Set**

The FAS will include all patients who receive at least one dose of study drug. Patients will be classified according to the study treatment actually received. If a patient receives more than one treatment the patient will be classified according to the first treatment received.

#### **4.2. Safety Analysis Set**

The safety analysis set will include all patients who receive at least one dose of study drug. Patients will be classified according to the study treatment actually received. If a patient receives more than one study treatment, the patient will be classified according to the first treatment received. In this non-randomized study, the FAS and the safety analysis set are identical.

#### **4.3. Other Analysis Set**

##### **4.3.1. DLT-evaluable Set**

The DLT evaluable set is a subset of the safety analysis set and will include all patients who are eligible, receive both study treatments and who either experience a DLT during the first 2 cycles of PF-05082566 or complete the two cycles' DLT observation period. Note that every patient will contribute to the determination of the MTD including patients who are lost to follow-up prior to completion of the two cycles' DLT observation period.

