3. STUDY DESIGN

3.1. Study Overview

This is a Phase 1b, open-label, multi-center, multiple-dose, safety, pharmacokinetic CCI study designed to estimate the maximum tolerated dose (MTD), and determine the Recommended Phase 2 Dose (RP2D) of PF-05082566 in combination with MK-3475 in patients with advanced solid tumors.

PF-05082566 will be administered as a 1-hour intravenous infusion q3wks. On Day 1 of each dosing cycle, in which the drugs are co-administered, the MK-3475 infusion will start 30 minutes after completion of PF-05082566 infusion and after the post- PF-05082566 and pre-MK-3475 PK blood samples are drawn.

A maximum of 45 patients will be treated during the dose escalation phase of this study.

Treatment with study drugs will continue until completion of 32 cycles (approximately 24 months) of treatment, confirmed objective disease progression, patient refusal, patient lost to follow up, unacceptable toxicity occurs, or the study is terminated by the Sponsor, whichever occurs first.

Safety will be monitored at regular intervals throughout the study by means of laboratory tests and clinical visits.

Antitumor activity will be assessed by radiological tumor assessments conducted at baseline, at 9 weeks, and every 6 weeks thereafter, whenever disease progression is suspected (eg, symptomatic deterioration), at the time of End of Treatment (if not done in the previous 6 weeks), and during follow-up visits, using RECIST version 1.1.

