9.1. Analysis Sets

1. Safety analysis set.

The safety analysis set includes all enrolled patients who receive at least one dose of study medication.

2. Full analysis set.

The full analysis set includes all enrolled patients.

3. DLT evaluable set.

All enrolled patients who are eligible, receive study treatment and who either experience a DLT during the first 2 cycles of PF-05082566, or complete the two cycles' DLT observation period. Note that every patient will contribute to the determination of the MTD including patients who are lost to follow-up prior to completion of the two cycles' DLT observation period.

4. Response analysis set.

All enrolled patients who are eligible, receive study treatment, have baseline tumor assessments and at least 1 on-study tumor assessment will be considered evaluable for response. Patients who are treated and removed from study prior to on-study tumor assessment because of disease progression will be considered evaluable for efficacy and counted as failures. Response analysis will be performed for both the safety analysis set and the response analysis set.

5. PK analysis sets.

The PK concentration population is defined as all enrolled patients treated who have at least one concentration of either PF-05082566 or MK-3475.

The PK parameter analysis population is defined as all enrolled patients treated who have at least 1 of the PK parameters of interest.

6. Biomarker Analysis set.

Treated patients who have baseline and at least 1 on study biomarker assessment will be considered evaluable.

7. ECG/QTc Analysis set

8. Treated patients who have baseline and at least 1 on study ECG/QTc measurement will be considered evaluable.

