9.6. Safety Analysis

Summaries and analyses of the primary safety endpoint will be based on the per protocol analysis set. Summaries and analyses of all other safety parameters will include all patients in the Safety Analysis Set.

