### 6.1. Primary Endpoints

#### 6.1.1. DLT

##### 6.1.1.1. Primary Analysis

The primary analyses will be based on the DLT-evaluable set. DLTs will be listed and summarized by treatment group.

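### SAP 4.3.1 drops a patient from the primary DLT summary when the DLT occurs before the first MK-3475 infusion

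*SAP*

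**What the plan says.** - **SAP 4.3.1** admits eligible patients who "receive both study treatments and who either experience a DLT during the first 2 cycles of PF-05082566" or who finish the two-cycle window. It then notes that "every patient will contribute to the determination of the MTD including patients who are lost to follow-up" before the window ends.
- **SAP 6.1.1.1**: "The primary analyses will be based on the DLT-evaluable set". The planned output is a listing and a summary by treatment group. SAP 5.2 names the same set for DLT summaries.
- **Protocol 9.1** defines the set with the same name as "All enrolled patients who are eligible, receive study treatment and who either experience a DLT" or complete the window. It has no explicit both-drugs condition.
- **Protocol 9.6** names another population: "Summaries and analyses of the primary safety endpoint will be based on the per protocol analysis set". Neither Protocol 9.1 nor SAP Section 4 defines it.
- **Protocol 3.1** fixes the order of dosing: "the MK-3475 infusion will start 30 minutes after completion of PF-05082566 infusion". SAP 2.2 says the same.

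**The concern.** The exposure condition applies to everyone in the SAP set, including patients who qualify because they had a DLT. Since PF-05082566 goes first, an early severe toxicity of the investigational drug can itself be the reason why MK-3475 is never given. The event that the endpoint is meant to count then removes the patient from the table that counts it.

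At stake is the reported DLT rate per dose level. Groups are small, so one missing case is visible, and the error runs one way: it makes the combination look better tolerated. The undefined population in Protocol 9.6 leaves a reader unable to tell from the protocol alone which patients the primary table should contain.

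**Working it through.** **Figures stated in the plan.** The documents do not say how many patients might be affected. The sample-size figures in SAP 5.1.1 are not at issue here, and the detection probabilities reproduce: 1 − 0.95^45 = 0.901 and 1 − 0.90^45 = 0.991, against the stated 0.90 and 0.99.

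**Step 1: is the event a DLT?** Protocol 3.3 and SAP 3.1 count a Grade 3 or higher non-laboratory toxicity in the first two cycles if it is attributable to one or both drugs. Attribution to PF-05082566 alone is enough. Both sections also list failure to complete two infusions of the two drugs in the window. So a Grade 3 or 4 reaction to the first PF-05082566 infusion qualifies.

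**Step 2: can that patient miss MK-3475 altogether?** PF-05082566 runs for 60 minutes and MK-3475 starts 30 minutes later, so on schedule the first 60 + 30 = 90 minutes pass before any MK-3475 is given. Protocol Table 12 ends trial treatment after a Grade 3 or 4 infusion reaction. Section 5.7.2 offers that table to sites without procedures of their own, so discontinuation is likely but not certain.

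**Step 3: does having a DLT waive the condition?** The SAP set has the structure: eligible AND received both AND (had a DLT OR completed the window). The DLT branch sits inside the exposure condition and does not waive it. SAP 3.4.1 uses the term study treatment for a dose cohort of the combination, so the phrase in 4.3.1 can only sensibly mean both drugs. The patient is out.

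**Step 4: the protocol set.** The structure is: eligible AND received study treatment AND (had a DLT OR completed the window). On its ordinary reading the patient is in.

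**Step 5: size in the crude table.** Take n patients at a dose with x DLTs, one of them before any MK-3475. The rate goes from x/n to (x − 1)/(n − 1), a fall of (n − x)/[n(n − 1)], which is never negative. The stopping rule (Protocol 3.2, SAP 5.1.1) makes n = 9 a natural illustration. The values of x are assumed.

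| All kept | One DLT patient dropped | Fall (points) |
|---|---|---|
| 1/9 = 11.1% | 0/8 = 0% | 11.1 |
| 2/9 = 22.2% | 1/8 = 12.5% | 9.7 |
| 3/9 = 33.3% | 2/8 = 25.0% | 8.3 |
| 4/9 = 44.4% | 3/8 = 37.5% | 6.9 |

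**The case against.** The gap is narrow. It needs a DLT before the first MK-3475 infusion, because a single MK-3475 administration satisfies the condition. An affected patient is not lost from the report: the safety set requires only one dose of study drug (SAP 4.2). The event would appear among Grade 3 or higher adverse events (SAP 6.6.1.1) and infusion-related reactions (SAP 6.6.4). Protocol 9.6.1 separately lists DLT events by dose level without a both-drugs condition.

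A crude summary in evaluable patients beside a model that uses everyone is also a coherent arrangement. The note in 4.3.1 and the weighting in SAP 5.1.2 are compatible with it, so the exclusion and the rule that all patients count for the MTD need not be called a contradiction.

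The per-protocol wording in Protocol 9.6 may be no more than a naming slip, since SAP 5.2 and 6.1.1.1 say which set is used. And Protocol 5.1 uses the term study drug for the two agents together, so the protocol's own set is less explicit than one would like.

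All of this limits the consequences, and I accept it. It does not remove the defect. The primary table, built as written, omits a true DLT, and the tables that retain the patient do not report the primary endpoint as a rate.

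**Conclusion.** The point holds in a limited form. Followed literally, SAP 4.3.1 removes from the primary DLT summary any patient whose DLT precedes the first MK-3475 infusion. The number is probably small and is unknown. If it is one patient among nine, the crude rate falls by about 7 to 11 points for one to four DLTs, for example from 22.2% to 12.5%. The undefined set in Protocol 9.6 is a separate, minor wording fault.

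A reader might infer three stronger conclusions. The documents do not support them.

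- **That the exclusion moves the MTD.** Fitting the power model to the SAP set, with the example prior rates, σ₀ = 1, and assumed data of 0/3 at 0.45, 0/3 at 0.9 and 2/9 at 1.8 mg/kg, gives 0.25^exp(−0.029) = 26.0% at 3.6 mg/kg. With 1/8 at 1.8 mg/kg it gives 0.25^exp(0.219) = 17.8%, so the highest dose estimated below 25% changes from 1.8 to 3.6 mg/kg. But the plan does not fit the model to that set: every patient contributes, and a patient with a DLT has full weight. The prior rates are only those of an example plot, and nobody has been treated at 3.6 mg/kg in this scenario. With 3/9 or 4/9 at 1.8 mg/kg, dropping one DLT leaves the selected dose unchanged.
- **That the plan provides no MTD estimate.** SAP 5.1.2 and Protocol 9.2 give the model, the posterior mean and the MTD rule, and Protocol 9.6.1 says that DLTs are used to estimate the MTD. What SAP Section 6 lacks is a line reporting the final fit and naming its data.
- **That leaving out DLT-free early leavers seriously inflates the rate.** With true rate p and a fraction d leaving evenly over the window, the crude rate is p(1 − d/2)/[p(1 − d/2) + (1 − p)(1 − d)]. For p = 25% this is 25.5% at d = 5%, 26.0% at 10% and 27.3% at 20%. The dropout values are assumptions, and the TITE-CRM uses these patients' partial follow-up.

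**What to change.** (a) **SAP 4.3.1**: include any patient who received at least one dose of either study drug and had a DLT in the window. Keep the both-drugs condition only for patients who qualify by completing the window without a DLT. Relaxing it for everyone would admit DLT-free patients exposed to one drug and dilute a combination rate. The eligibility condition is common to both documents and is a separate choice. Whatever is decided there should apply equally to patients with and without a DLT.

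(b) **SAP 6.1.1.1**: alongside the crude table, report the final TITE-CRM fit in all treated patients, with partial weights for incomplete follow-up. Give the posterior DLT probability and credible interval at each dose, and the resulting MTD.

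(c) **Protocol 9.6**: replace the reference to the per-protocol set with the DLT-evaluable set.

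The cost is a few lines in the SAP and one sentence in the protocol. No new data are needed and patient management does not change. The model already guides the dosing decisions of the Dose-Escalation Steering Committee (Protocol 9.7, SAP Section 7).
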